9.3.4.2 Safety outcome definitions

Cohort 1:

NPR lacks information on laboratory measurements. Hence, we cannot use the ISTH (International Society of Thrombosis and Hemostasis) definition of a major bleeding episode which include a fall in hemoglobin level of 20 g/L (1.24 mmol/L) or more

The primary bleeding endpoint of intracranial haemorrhage (ICH) is defined by the following ICD10 codes:

I60x Subarachnoid haemorrhage

I61x Intracerebral haemorrhage

I62x Other non-traumatic intracranial haemorrhage

Cohort 2:

The primary bleeding endpoint of intracranial haemorrhage (ICH) is defined by the following ICD10 codes:

I60x Subarachnoid haemorrhage

I61x Intracerebral haemorrhage

I62x Other non-traumatic intracranial haemorrhage

Secondary safety outcome measures in cohort 2 are major bleeds defined by the Cunningham algorithm (11) and the ISTH definition (12) for major bleeds.

The Cunningham algorithm (11) defines a hospitalization with a primary ICD10 code for major bleeding except for ICH where all hospitalizations is counted (> 8 hrs in-patient)(see below).

The Cunningham algorithm is originally based on the ICD-9-CM system. All codes in the ICD-9-CM is not easily converted to ICD9 and later the ICD9 system was replaced by ICD10. Thus, the ICD10 based Cunningham definition will be built on the following outcomes:

Gastrointestinal:

K920	Hematemesis
K921	Melena
K922	Gastrointestinal haemorrhage, unspecified
K226	Mallory-Weiss syndrome
K250/K252/K254/K256	Gastric ulcer with bleeding and/or perforation
K260/K262/K264/K266	Duodenal ulcer with bleeding and/or perforation
K275/K272/K274/K276	Peptic ulcer with bleeding and/or perforation
K285/K282/K284/K286	Peptic ulcer with bleeding and/or perforation
K290	Acute haemorrhagic gastritis
K625	Haemorrhage of anus and rectum
I850	Oesophageal varices with bleeding
I983	Oesophageal varices with bleeding in diseases classified elsewhere

Intracranial:

I60x	Subarachnoid haemorrhage
I61x	Intracerebral haemorrhage
I62x	Other non-traumatic intracranial haemorrhage

Other:

N02	Recurrent and persistent haematuria
H431	Vitreous hemorrhage
K661	Haemoperitoneum
R042	Haemoptysis
R040	Epistaxis
K250	Haemarthrosis
N939	Vaginal bleeding

The ISTH (12) definition for major bleeding in non-surgical patients is defined by one of the following criteria:

1. Fatal bleeding, and/or
2. Symptomatic bleeding in a critical area or organ, such as intracranial, intraspinal, intraocular, retroperitoneal, intraarticular or pericardial, or intramuscular with compartment syndrome (from ICD10 codes in NPR), and/or
3. Bleeding causing a fall in hemoglobin level of 20 g/ L (1.24 mmol/L) or more, or leading to transfusion of two or more units of whole blood or red cells (from EMR data).

Organ system divided analyses (intracranial hemorrhage, gastrointestinal bleeding etc.) will be analyzed separately.

9.4 Data sources

For cohort 1 three data sources will form the basis for the analyses, the Norwegian Census Register (FRG), the Norwegian Prescription Database (NorPD) and the Norwegian Patient Register (NPR). The FRG list all Norwegian residents from birth to death, including migration data and place of birth.

The NorPD is a register covering all prescriptions dispensed at pharmacies nationwide and data is available from 1 January 2004. Each medication is coded according to the Anatomical Therapeutic Chemical (ATC) system. The prescription registry also includes information about date of dispensation, quantity dispensed, the defined daily dose (DDD) of the dispensed drug and strength. NorPD does not cover drug administered during hospital stays, drugs used at nursing home or over-the-counter drugs. From March 2007 the NorPD includes the reimbursement code using either the ICD10 or the ICPC-2 coding systems.

The NPR was established in 2008 and contains all hospital visits (emergency visits, in-patient hospitalizations and outpatient ambulatory consultations), length of stay and procedures (surgical and medical) from all hospitals in Norway. Diagnoses are coded according to the International Classification of Diseases, 10th revision (ICD10). Medical and surgical procedures are coded based on the NOMESCO (The Nordic Medico-Statistical Committee) coding system. Both primary and all subsequent codes related to each admission will be retrieved. Lag time in NPR is approximately 4 months.

The registries are nation-wide and provision of the information is mandatory, which eliminates the risk of both selection and recall bias. The large and detailed dataset also makes it possible to adjust for risk factors and analyze in depth the different sources of bias and confounding. The registry holders will generate the datasets and release it in a coded and de-identified form, but with a unique identifier common to the three datasets making individual merging of the NorPD, NPR and FRG datasets possible.

Data from the registries will be linked using the unique 11-digit national identification number. NorPD is a pseudonymized register and the registry holder will according to national guidelines handle the linkage and release the dataset in a coded form so that all participants remain de-identified.

The following key variables will be retrieved from FRG;

- Age
- Gender (male, female)

The following key variables will be retrieved from de-identified EMR data;

- Anthropometric data (height and weight)
- Laboratory values

- Deeper level longitudinal data on diagnoses and treatments, including referrals from primary care physicians.

These data will complement the data from the national registers.

9.5 Study size

There is no underlying hypothesis to confirm or reject. The sample is determined by eligibility. However it is desirable to assess the suitability of the available sample to produce useful estimates of the main outcomes.

The ratio of dispensations between the different NOACs and warfarin is estimated based on average number of dispensations in the period of 2014-2016 as given by NorPD statistics. Approximately half of patients treated with OAC have a dispensation for warfarin, 17%, 19% and 11% for apixaban, rivaroxaban and dabigatran respectively (Table 6). Based on previous studies, we estimate the risk of ischemic stroke and intracranial hemorrhage in the warfarin group, during an assumed mean follow-up of 18 months, to be 2.43% and 1.23% respectively.(1-4, 13-15)

ATC code and drug	2013	2014	2015	2016
	B01AA03- warfarin	87,994	77,755	69,289
B01AF02 – apixaban	2,260	8,640	21,507	37,276
B01AF01 – rivaroxaban	13,423	20,795	25,480	28,924
B01AE07 - dabigatran	13,879	15,358	13,843	13,327
Total	117,556	122,548	130,119	139,884

Table 6: Number of patients with at least one dispensation of an OAC annually in the period 2013 to 2016 as given by NorPD. The table gives the total OAC use for all indications.

The study population will comprise all adult OAC naïve NVAF patients in Norway who filled a prescription for an OAC (rivaroxaban, apixaban, dabigatran, warfarin) in the study period, defined as from 1 January 2014 to 30 June 2018 (or later depending on availability of data). Based on Table 6 demonstrating the total number of new prescriptions for OACs in 2013-2016 and based on a publication describing Norwegian NVAF patients, the sample size of naïve patients available for the study will be approximately 70,000 patients; however, as known from previous unpublished data, the proportion of naïve patients who get prescribed a NOACs is likely to be increasing in the last several years.

The tables below show the precision for the proportions and relative risks of ischemic stroke and intracranial hemorrhage that might be expected in terms of width of 95% confidence intervals.

Assuming that 90% of dabigatran, apixaban or rivaroxaban patients can be propensity score matched with patients treated with warfarin, the 95% confidence intervals for the matched proportions show a sufficient precision for ischemic stroke and intracranial hemorrhage (see tables below).

1:1 propensity score matched with warfarin			
Incidence rate	dabigatran N=6930	apixaban N=10710	rivaroxaban N=11970
1.46%	(1.19%, 1.77%)	(1.24%, 1.70%)	(1.25%, 1.69%)
1.94%	(1.62%, 2.29%)	(1.69%, 2.22%)	(1.70%, 2.20%)
2.43%	(2.08%, 2.81%)	(2.14%, 2.74%)	(2.16%, 2.72%)
2.92%	(2.53%, 3.34%)	(2.61%, 3.26%)	(2.63%, 3.24%)
4.37%	(3.90%, 4.88%)	(3.99%, 4.77%)	(4.01%, 4.75%)

Table 7: Two sided exact (Clopper-Pearson) 95% Confidence Intervals for the proportions of ischemic stroke; SAS 9.2;

The widths of the 95% confidence intervals for the incidence rates for ischemic stroke are not exceeding 0.98%, indicating a sufficient precision.

1:1 propensity score matched with warfarin			
Relative Risk compared to warfarin	dabigatran N=6930	apixaban N=10710	rivaroxaban N=11970
0.60	(0.47, 0.77)	(0.49, 0.73)	(0.50, 0.72)
0.80	(0.64, 1.01)	(0.67, 0.96)	(0.68, 0.95)
1.00	(0.81, 1.24)	(0.84, 1.19)	(0.85, 1.17)
1.20	(0.98, 1.47)	(1.02, 1.41)	(1.03, 1.40)
1.80	(1.50, 2.17)	(1.55, 2.09)	(1.56, 2.07)

Table 8: 95% confidence intervals for relative risks for ischemic stroke with an assumed proportion of 2.43% for warfarin. The number of warfarin patients was assumed to be equal to the corresponding NOAC; SAS 9.2;

The widths of the 95% confidence intervals for the relative risks for the matched populations are not exceeding 0.67.

1:1 propensity score matched with warfarin			
Incidence rate	dabigatran N=6930	apixaban N=10710	rivaroxaban N=11970
0.74%	(0.55%, 0.97%)	(0.58%, 0.92%)	(0.60%, 0.91%)
0.98%	(0.76%, 1.24%)	(0.80%, 1.19%)	(0.81%, 1.17%)
1.23%	(0.98%, 1.51%)	(1.03%, 1.46%)	(1.04%, 1.44%)
1.48%	(1.21%, 1.80%)	(1.26%, 1.73%)	(1.27%, 1.71%)
2.21%	(1.87%, 2.58%)	(1.94%, 2.51%)	(1.96%, 2.49%)

Table 9: Two sided exact (Clopper-Pearson) 95% Confidence Intervals for the proportions of intracranial hemorrhage; SAS 9.2;

The widths of the 95% confidence intervals for the incidence rates for intracranial hemorrhage are not exceeding 0.71%, indicating a sufficient precision.

1:1 propensity score matched with warfarin			
Relative Risk compared to warfarin	dabigatran N=6930	apixaban N=10710	rivaroxaban N=11970
0.60	(0.42, 0.85)	(0.45, 0.79)	(0.46, 0.78)

0.80	(0.58, 1.10)	(0.62, 1.03)	(0.63, 1.02)
1.00	(0.74, 1.35)	(0.79, 1.27)	(0.80, 1.26)
1.20	(0.90, 1.60)	(0.95, 1.51)	(0.97, 1.50)
1.80	(1.38, 2.34)	(1.45, 2.22)	(1.48, 2.20)

Table 10: 95% confidence intervals for relative risks for intracranial hemorrhage with an assumed proportion of 1.23% for warfarin. The number of warfarin patients was assumed to be equal to the corresponding NOAC; SAS 9.2;

The widths of the 95% confidence intervals for the matched relative risks are not exceeding 0.96.

9.6 Data management

There will be 3 main steps;

- Merge together all data and build the analytical dataset
- Create patient cohorts
- Populate tables and figures

Statistical Analysis System (SAS software, version 9.4, SAS Institute, Cary, NC) will be used to all data handling to prepare analytical dataset.

The data from NorPD and NPR are considered high quality register data, however, some quality checking and data cleaning will be done to check for reasonability and consistency of data, e.g. by cross-tabulation of patient characteristics compared to publically available data sources and so forth. From these initial cut of data, further programming will be applied to identify the eligible patient cohorts with additional information of interest to address study objectives as include the following:

- All data from different sources will be retrieved/imported into SAS.
- Completeness of data regarding the number of variables and observations will be verified against the source.
- Quality control of the reasonability and consistency of information and data cleaning will be done
- Datasets will be merged to provide all information needed from various sources to define the patient cohorts.
- Patient cohorts will be defined and include all subjects which fulfills the cohort's inclusion criteria (section 9.2.2).
- Co-morbid conditions of interest within five years prior to index date will be identified, and various co-morbidity scores will be calculated (section 9.3.1).
- Concomitant medications at baseline and during the follow-up according to the ATC codes as described in section 9.3.1 will be selected.

- Adherence to each OAC will be estimated as described in section 9.3.3.
- All outcomes of interest (new events during follow-up) will be selected according to sections 8.1-3 and 9.3.4.1-2.
- Three different subset of cohorts for survival analysis based on exposure to OAC (continuous use or switched) will be defined as described in section 9.3.2.
- Finally a clean ready-to-use analysis database will be constructed, which will contain complete set of all data including the derived variables, according to the study protocol.
- Tables and figures will be populated

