9.2 Setting

The study will be undertaken in Norway and will comprise all adult patients with NVAF who initiated treatment with either a NOAC or warfarin during the study period for the first time (OAC naïve first-time users). Study endpoints, discontinuation, switch to another OAC, death or end of study period will serve as censoring criteria.

The NVAF study population is defined in accordance with the 2018 European Heart Rhythm Association practical guide on the use of non-vitamin K antagonist oral anticoagulants in patients with atrial fibrillation, which define NOAC eligibility in NVAF patients as atrial fibrillation in the absence of rheumatic mitral stenosis or a mechanical heart valve.

Cohort 1 (registry study): Registries in Norway are nation-wide and provision of the information is mandatory, which eliminates the risk of both selection and re-call bias. The large and detailed dataset also makes it possible to adjust for other risk factors on which information is available.

In cohort 2, patients with NVAF diagnosis will be identified through extraction of patient-level data from EMRs from a number of hospitals in Norway, in order to describe these patients more closely regarding their clinical characteristics that are not available in nation-wide registers (e.g., in-patient treatments, anthropometric data and laboratory test results). This part of the

¹ Source: <http://www.legemiddelverket.no>

study is a pilot that will test the operational feasibility of accessing and linking the regional EMR data to the Norwegian Health Registers. Should the access to the regional EMR be granted, patients in cohort 2 will be identified and their EMRs extracted using the Pygargus Customized Extraction Platform (CXP). The extraction program has been used in a number of research projects since 2005 in the Swedish and Norwegian health care systems (6, 7). De-identified individual level data on age, gender, prescriptions, diagnoses, measures, laboratory tests, health care professional (HCP) visits, referrals, etc. can be collected from the EMRs into an encrypted database.

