The duration of dispensation (DoD) will be set as the date of a dispensed prescription plus the estimated duration of that prescription (duration of OAC supply estimated from the dispensed pack-size and strength).

The following rules applies:

1. If the next dispensed prescription was for the same OAC within 30 days after end of DoD there was a continuous treatment
2. If a new dispensed prescription for another OAC occurred within DoD or within 30 days after end of DoD there was a switch in OACs (switching date = date of dispensation)
3. If the next dispensed prescription was for the same OAC more than 30 days after end DoD there was a discontinuation (discontinuation date = date of DoD + 30 days)

A 30-day gap period is included to take into account incomplete adherence to treatment. The figure underneath displays the three different scenarios. In sensitivity analyses the gap period will be varied from 30 days to 0 days, 15 days and 60 days, respectively.

[figure not shown]

Figure 4: Definition of continuation, switch and discontinuation

Patients to be included in the effectiveness and safety analysis should have a supply of OAC covering the event, plus a 30 days grace period for those patients discontinuing their therapy. Any event happening after the date of discontinuation plus 30 days or after a switch in OAC therapy will not be included.

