9.7 Data analysis

All data analyses will be performed using SAS statistical software version 9.4., and will be reported in a manner consistent with the Strengthening the Reporting of Observational Studies in Epidemiology (STROBE) guidelines.

Descriptive statistics will be used to present the data where continuous variables will be summarized as mean, standard deviation, median, minimum and maximum. Categorical variables will be described by frequencies and related percentages. Summaries will be reported separately for the elderly +75 years (cohort 1 and 2) and patients with renal impairment (cohort 2). Annual frequency of different OAC treatment during the study period in addition to adherence to each NOACs (high, moderate, low, and poor) will be presented. Also a separate analysis will be done to characterize patients with NVAf who have not been treated with OAC.

In the following, cohort 1 (registry) and cohort 2 (EMR) will be analyzed separately, but using the same analytical approaches.

The analyses will be performed on the total sample as well as on a confounder adjusted sample. It has to be kept in mind that analyses based on the overall sample (non-confounder adjusted sample) is prone to bias (see section 9.9).

Three separate propensity score models will be conducted and a 1:1 matching will be performed for:

- warfarin vs apixaban
- warfarin vs dabigatran
- warfarin vs rivaroxaban.

No matching to compare the NOACs among each other (e.g. apixaban vs rivaroxaban) will be performed due to underlying differences in prescribing preferences of different NOACs.

The propensity scores (PS) will be based on demographic variables and clinically relevant medical history, e.g. cardiovascular risk factors, comorbidities and concomitant medications at baseline.

Patients who switch or discontinue the OAC treatment will be censored at the date of switch or discontinuation. It cannot be ruled out that the switch of OAC (censoring) could be informative, but it is handled as uninformative censoring in the analyses.

Detailed methodology for propensity score modeling, matching, handling of missing data, summary and statistical analyses in this study will be documented in a Statistical Analysis Plan (SAP), which will be dated, filed and maintained by the sponsor. The SAP may modify the plans outlined in the protocol; any major modifications of primary endpoint definitions or their analyses would be reflected in a protocol amendment.

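### Section 9.6 forms survival-analysis subsets by later continuous use or switching, while 9.2, 9.2.1 and 9.7 censor at switch or discontinuation and 9.7.1 mentions neither

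*Protocol*

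**What the plan says.** The data-management steps in Protocol 9.6 first build patient cohorts from the inclusion criteria. A later step adds a further division: "Three different subset of cohorts for survival analysis based on exposure to OAC (continuous use or switched) will be defined as described in section 9.3.2". It announces three subsets but names only two states.

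The section it points to, 9.3.2, sets rules for the next dispensation:
- Continuation: "If the next dispensed prescription was for the same OAC within 30 days after end of DoD there was a continuous treatment".
- Switch: "If a new dispensed prescription for another OAC occurred within DoD or within 30 days after end of DoD there was a switch in OACs".
- Discontinuation: the same drug is next dispensed more than 30 days after supply ends.

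It sums these up with "The figure underneath displays the three different scenarios" and adds a rule for counting events: "Any event happening after the date of discontinuation plus 30 days or after a switch in OAC therapy will not be included".

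Elsewhere switching is a censoring event. Section 9.2: "Study endpoints, discontinuation, switch to another OAC, death or end of study period will serve as censoring criteria". Section 9.2.1 repeats this for switch and discontinuation. Section 9.7: "Patients who switch or discontinue the OAC treatment will be censored at the date of switch or discontinuation". Section 9.7 also forms its three matched comparisons by drug, each NOAC against warfarin. Section 9.7.1 runs person-time from first OAC use to the outcome, death or the end of follow-up, and lists neither switch nor discontinuation.

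**The concern.** Whether a patient is a continuous user or a switcher can be read only from dispensations after the index date. Sorting whole patients into survival-analysis sets by that status, with time counted from index, uses future information.

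- **Switched subset.** A patient must stay event-free on the index drug until the switch to enter it, so the time from index to switch is immortal. Under the event rule in 9.3.2, which drops everything after a switch, this subset could show no events at all.
- **Continuous subset.** It keeps every event that came before any switch, but loses the event-free time that later switchers contributed before switching. Its rate is too high.

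The excess grows with the switching rate. If warfarin and a NOAC differ in switching, a comparison within continuous users would show a difference that the drugs did not cause.

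**Working it through.** **Step 1. The passages side by side.**

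| Section | How later switching or discontinuation is handled |
|---|---|
| 9.2, 9.2.1, 9.7 | All initiators kept; censored at switch or discontinuation |
| 9.3.2 | Three dispensing scenarios with dates; events after a switch not counted |
| 9.6 | Three subsets for survival analysis by continuous use or switching, defined by reference to 9.3.2 |
| 9.7.1 | Person-time to outcome, death or end of follow-up; switch and discontinuation not listed |

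The reference from 9.6 to 9.3.2 does not resolve: the three items there are refill patterns, not groups of patients. Rows 1, 3 and 4 give different risk sets or different person-time.

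**Step 2. What a literal reading of 9.6 would do.** The plan states no figure to reproduce here, so this is an illustration.

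Input from the protocol (9.5): warfarin ischemic stroke risk of 2.43% over a mean of 18 months. With a constant hazard, λ = −ln(1 − 0.0243)/1.5 = 0.0164 per year, or 1.64 per 100 patient-years.

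Assumptions that are not in the protocol: the same λ on both drugs (true ratio 1.00); switching independent of the event, at a constant rate σ of 0.20 per year on warfarin and 0.05 on a NOAC; no deaths and no discontinuation.

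With h = λ + σ and horizon τ = 1.5 years, per patient:
- Events before switch: E = (λ/h)(1 − e^(−hτ))
- Person-time, all initiators censored at switch: A = (1 − e^(−hτ))/h
- Person-time, never-switchers only: B = λ[1/h² − e^(−hτ)(τ/h + 1/h²)] + τe^(−hτ)

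| | σ = 0.05 | σ = 0.20 |
|---|---|---|
| h | 0.0664 | 0.2164 |
| E | 0.02341 | 0.02101 |
| A | 1.4277 | 1.2809 |
| B | 0.0173 + 1.3578 = 1.3751 | 0.0149 + 1.0842 = 1.0991 |
| E/A per 100 patient-years | 1.64 | 1.64 |
| E/B per 100 patient-years | 1.70 | 1.91 |

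Censoring as in 9.7 gives 1.64/1.64 = 1.00. Keeping only never-switchers gives 1.70/1.91 = 0.89.

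**Step 3. Sensitivity to follow-up.** With follow-up spread evenly over 1 to 54 months (the span from January 2014 to June 2018), averaging the same quantities gives 1.77 and 2.20 per 100 patient-years, a ratio of 0.80. That spread averages (1 + 54)/2 = 27.5 months before switching, longer than the protocol's 18-month mean, so 0.89 is closer to the protocol's own assumption.

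**Step 4. Sensitivity to direction.** If the NOAC group switches at 0.20 and warfarin at 0.05, the ratios become 1/0.89 = 1.12 and 1/0.80 = 1.25. With equal switching the ratio is 1.00.

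**Step 5. Scale.** At a relative risk of 1.00, Table 8 gives intervals of 0.81 to 1.24 (dabigatran), 0.84 to 1.19 (apixaban) and 0.85 to 1.17 (rivaroxaban). A shift to 0.89 lies inside all three and a shift to 0.80 lies outside all three. Either would be systematic error that more patients do not remove.

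**The case against.** The strongest reply is that 9.6 is a data-management checklist and the bullet loosely describes the step that derives exposure status and censoring dates. Section 9.3.2 assigns those dates and counts events on treatment; nothing in it removes a later switcher's earlier person-time. Sections 9.2, 9.2.1 and 9.7 are explicit about censoring. No outcome comparison among continuous users or among switchers appears in 9.7, 9.7.1 or 9.7.2, and a switched set that can hold no events is hardly a credible planned analysis. The SAP, which is not shown, may say how the subsets are used.

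Much of this stands. It rules out saying that the primary comparison is planned on these subsets. It does not remove the conflict: the bullet says that the subsets are for survival analysis, it comes in addition to the cohort-building step, and its cross-reference leads to no definition. Section 9.7.1 does not settle the matter, because its person-time definition leaves out the censoring events.

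A reader might also infer from Table 6 that warfarin users switch far more, so that any bias runs against warfarin. Warfarin users fall from 87,994 in 2013 to 139,884 − 37,276 − 28,924 − 13,327 = 60,357 in 2016, while apixaban users rise from 2,260 to 37,276. But the table counts everyone with at least one dispensation in the year, for all indications. It does not isolate OAC-naïve NVAF initiators and does not count switches. Fewer new warfarin starts, deaths and stopping would also lower the count, and 9.5 itself says that the share of naïve patients prescribed a NOAC is probably rising.

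**Conclusion.** The point holds as an inconsistency that permits a biased analysis. Section 9.6 states a subset rule based on information from after the index date, its cross-reference does not define the subsets, and it conflicts with the censoring in 9.2, 9.2.1 and 9.7; the person-time definition in 9.7.1 agrees with neither. Programmed literally, 9.6 would bias the survival rates, and differently by drug if switching differs.

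The size and direction of any bias are unknown, because the protocol gives no switching rate for any drug. The ratios of about 0.89 and 0.80 rest on assumed switching of 20% against 5% per year, constant independent hazards, no competing discontinuation or death, and the dropping of later switchers, which the protocol nowhere spells out. The documents do not support the stronger reading that the planned warfarin-NOAC comparison is biased, or biased against warfarin.

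**What to change.** Replace the bullet in 9.6 with: *Survival-analysis cohorts are defined only by the OAC dispensed at the index date; switch and discontinuation are time-dependent censoring events (9.7).*

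In 9.7.1, add switch and discontinuation to the events that end person-time, so that it matches 9.2, 9.2.1 and 9.7.

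If a separate analysis of switchers is wanted, start its follow-up at the switch date. If one of persistent users is wanted, start it at a landmark (for example, event-free and still on the index drug at 6 months) and count only later events and time.

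The cost is two short text changes and the matching dataset specification, with no extra data. It should be settled before the analysis dataset is programmed.
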